Effects of SinuSonic on Psychological and Physical Well-Being

NCT number NCT06268730
Document Date 12/26/2023

Effect of the SinuSonic Device on Psychological and Physical Well-Being in Adults with Nasal/Sinus Congestion
PI (UNC): [name]

Brief background: Chronic nasal congestion impacts the functioning of the ventral vagal complex (VVC), which includes cranial nerves of the face and head (special visceral efferents), along with vagal regulation of the heart and lungs. Physiological compromise of the VVC due to a current or previous adverse experience may allow for worsening nasal congestion, which then has a circular impact back to poorer vagal regulation of the lungs.

This chronic cycle of congestion and poor vagal regulation can likewise impact mental health. Defensive symptoms/behaviors, such as anxiety and depression, are common emergent symptoms of a compromised VVC.

Purpose: The first aim of the study is to evaluate relationships between current/previous adverse events, degree of nasal congestion, perception of autonomic regulation and symptoms of anxiety and depression via self-report questionnaires.

The second aim of the study is to evaluate the effect of the SinuSonic on physical and psychological well-being in individuals with chronic nasal congestion. The SinuSonic is a self-applied nasal device designed to enhance physical well-being by reducing nasal congestion via simultaneous administration of acoustic vibration and gentle oscillating expiratory pressure. The vibration and expiratory pressure stimulate several cranial nerves that are included in the ventral vagal complex (VVC), including the cranial nerves of the face and head (special visceral efferents). According to the Polyvagal Theory (Porges, 1995, 1998, 2001, 2003, 2007), when the VVC is stimulated, the functioning of related cranial nerves and emergent behaviors should improve, supporting a calmer, more regulated nervous system, and improved mental health.

To evaluate the effects of the SinuSonic, self-report questionnaires will be administered (via RedCap) prior to beginning use of the SinuSonic, weekly during directed use of the SinuSonic (2 minutes per day, 2 times per day), and after 5 weeks of use of the SinuSonic. Weekly self-report questionnaires will include amount of SinuSonic usage and degree of nasal congestion. The final, 5-week questionnaires will include degree of nasal congestion, perception of autonomic regulation and symptoms of anxiety and depression.

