The VVC is based on the documented neuroanatomical and neurophysiological pathways between the brainstem areas that regulate the muscles of the face (via special visceral efferent pathways) and the heart and lungs (via the vagus). Features of the VVC may serve as a clinical checklist converging on symptoms of anxiety and depression as observed in several clinical disorders including autism (Bal et al., 2010; Patriquin et al., 2011; Porges et al., 2012; Van Hecke et al., 2009), Fragile-X-Syndrome (Heilman et al., 2011), selective mutism (Heilman et al., 2012), prematurity (Doussard-Roosevelt, et al., 1997), prenatal exposure to opiates and alcohol (Suess et al. 1997), PTSD (Sahar et al., 2001), perpetrators of domestic abuse (Umhau et al., 2002), Borderline Personality Disorder (Austin et al., 2007), behavioral regulation problems (Dale et al., 2011), and abuse and neglect (Dale et al., 2009). However, relating symptoms of anxiety and depression to an illness that impacts the functioning of the VVC (i.e., nasal congestion impacts the functioning of the vagus at the lungs) is a novel aspect of the current study.

Additionally, individuals who already have a compromised VVC due to adverse events (history or current), may also be at risk for the continued cycle of VVC complications (i.e., chronic congestion, anxiety and/or depression).

In summary, the function of the SinuSonic (i.e., reducing nasal congestion while improving vagal regulation of the lungs) align with the theoretical principles of the Polyvagal Theory. Thus, our proposed research will serve to determine whether the SinuSonic will have a significant impact on the reduction and management of physical and psychological symptoms (i.e., anxiety and depression), as they are described within the context of a dysregulated VVC.

Flowchart of Research Procedures:

Participants

50 adults (aged 18-99 years) with self-reported nasal congestion will be recruited for the study. Participants must be US residents.

Data Collection Procedures

Step 1: Recruit/Eligibility Screening

Individuals who make a purchase of the SinuSonic device will receive a recruitment flyer in the shipping box for their device, but only new users of the SinuSonic will be eligible to participate. The recruitment flyer will contain a QR code that users can scan to access the Eligibility Screening for the study in RedCap. Staff at SinuSonic has agreed to include the recruitment flyer when shipping packages.

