Short-Form Health Survey-12 (Ware et al., 1995). The SF-12 is a health-related quality-of-life questionnaire consisting of twelve questions that measure eight health domains to assess physical and mental health. Physical health-related domains include General Health (GH), Physical Functioning (PF), Role Physical (RP), and Body Pain (BP)

Total Nasal Symptom Score. The Total Nasal Symptom Score (TNSS) is the sum of scores for each of nasal congestion, sneezing, nasal itching, and rhinorrhea at each time point, using a four point scale (0–3), where 0 indicates no symptoms, a score of 1 for mild symptoms that are easily tolerable, 2 for awareness of symptoms which are bothersome but tolerable and 3 is reserved for severe symptoms that are hard to tolerate and interfere with daily activity. TNSS is calculated by adding the score for each of the symptoms to a total out of 12.

Adverse Traumatic Experiences Scale (ATES) (Kolacz et al., 2020). This measure asks about childhood adverse experiences, childhood maltreatment, other person maltreatment, life-threatening situations, sudden deaths of close ones, and personal health situations. Respondent-reported prior adverse events

of maltreatment, life-threatening situations, and sudden deaths of close ones are summed to create an adversity score (range: 0–19).

Patient Global Impression of Change (PGIC) (Hurst & Bolten (2004). The self-report measure Patient Global Impression of Change (PGIC) reflects a patient's belief about the efficacy of treatment. PGIC is a 7 point scale depicting a patient's rating of overall improvement. Patients rate their change as "very much improved," "much improved," "minimally improved," "no change," "minimally worse," "much worse," or "very much worse."

Data Analyses

Questionnaire data will be entered by participants into RedCap for researcher access. Researchers will export the data into SPSS for data analyses. All databases will be stored on password protected computers, accessible only to researchers affiliated with the study, and backed up on UNC servers.

As the current proposal is for a feasibility/pilot study, researchers will evaluate the following aims to determine whether a larger, randomized trial is warranted.

Aim 1: Examine associations between nasal congestion, autonomic functioning, adverse events, and mental health indices (depression, anxiety) at baseline. Pearson correlation analyses will be used to evaluate relationships among measures at each timepoint.

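### Aim 1 describes the baseline congestion–mood association by unadjusted correlations only; adding an ATES-adjusted estimate is a nearly free improvement, because the protocol's own theory places adversity upstream of both.

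*Combined protocol and SAP*

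**What the plan says.** Data Analyses, Aim 1, sets the task: "Examine associations between nasal congestion, autonomic functioning, adverse events, and mental health indices (depression, anxiety) at baseline". The method is one sentence: "Pearson correlation analyses will be used to evaluate relationships among measures at each timepoint". The aim has no stated hypothesis, significance level or rule for interpreting the correlations.

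The theory gives adversity a specific place:

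- Brief background, adversity to congestion: "Physiological compromise of the VVC due to a current or previous adverse experience may allow for worsening nasal congestion".
- Brief background, compromised ventral vagal complex (VVC) to mood: "Defensive symptoms/behaviors, such as anxiety and depression, are common emergent symptoms of a compromised VVC".
- Background, both together: people whose VVC is already compromised by adverse events "may also be at risk for the continued cycle of VVC complications (i.e., chronic congestion, anxiety and/or depression").

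The Background describes "relating symptoms of anxiety and depression to an illness that impacts the functioning of the VVC", with nasal congestion as the example, as a novel aspect of the study.

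Step 3 collects TNSS, HADS, BPQ, ATES and a demographic form at week 0. Description of Measures gives ATES a single sum score from 0 to 19. The only other planned analysis that names adversity is Aim 3, which treats it as a mediator of week-5 outcomes. That analysis does not adjust the baseline congestion–mood association.

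**The concern.** If adversity raises both congestion and anxiety/depression, the two will correlate even when neither affects the other. A pairwise correlation cannot separate that shared part from a relation between congestion and mood as such. The planned text does not commit to any estimate that does.

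The distinction matters for how the result is used. Data Analyses says the aims are evaluated to decide whether a larger randomized trial is warranted, and Aim 1 is among them. If adversity alone linked congestion and mood, relieving congestion would not be expected to change mood through that link. A raw correlation taken at face value could make the rationale for a device trial with mood outcomes look stronger than it is.

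**Working it through.** The plan gives no power, effect size or alpha for Aim 1, so there is no figure to reproduce. What follows illustrates size under stated assumptions.

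**Inputs**

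- From the documents (Participants): n = 50, "50 adults (aged 18-99 years) with self-reported nasal congestion will be recruited for the study".
- Assumed: two-sided 5% test.
- Assumed: correlation of adversity with the nasal score (a) and with HADS (b), from 0.3 to 0.6.
- Assumed: no direct congestion–mood link.
- Assumed: ATES either error-free or with reliability 0.8.

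**Step 1: induced correlation.** If adversity is the only source of the link, the raw correlation is r = a × b. For example, 0.5 × 0.5 = 0.25. At n=50 the critical value is |r| = 0.279.

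**Step 2: chance that the raw r is significant.** By Fisher z, with Φ the standard normal distribution function,

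P = Φ(atanh(r)·√(n−3) − 1.96) + Φ(−atanh(r)·√(n−3) − 1.96).

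For r = 0.25: atanh(0.25) = 0.255, √47 = 6.856, and the product is 1.751. The first term is Φ(−0.209) = 0.417; the second is negligible. So P is about 0.42.

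**Step 3: the adjusted estimate.** The partial correlation of congestion (C) and mood (M) given adversity (A) is

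r(CM·A) = [r(CM) − r(CA)·r(MA)] / √{[1 − r(CA)²]·[1 − r(MA)²]}.

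With error-free ATES the numerator is a×b − a×b = 0. With reliability 0.8, each observed ATES correlation shrinks by √0.8, so the product removed is 0.8 × a × b. At a = b = 0.5 the residual is (0.25 − 0.20)/(1 − 0.20) = 0.0625. At 0.6 it is (0.36 − 0.288)/(1 − 0.288) = 0.10.

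**Results** (percentage of studies significant; simulation with 20,000 normal replicates per row)

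| a, b | raw r | raw, Fisher z | raw, simulated | adjusted, error-free ATES | adjusted, reliability 0.8 |
|---|---|---|---|---|---|
| 0.3, 0.3 | 0.09 | 9.5 | 9.6 | 5.0 | 5.3 |
| 0.3, 0.5 | 0.15 | 17.9 | 18.3 | 4.8 | 5.6 |
| 0.4, 0.4 | 0.16 | 19.8 | 20.4 | 5.0 | 5.8 |
| 0.5, 0.5 | 0.25 | 41.7 | 42.0 | 4.9 | 6.9 |
| 0.6, 0.6 | 0.36 | 73.4 | 74.1 | 4.9 | 10.6 |

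At weaker correlations of 0.2 and 0.3, r = 0.06 and Fisher z gives about 7%, close to nominal.

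**Step 4: what adjustment costs.** The Fisher z standard error goes from 1/√47 = 0.146 to 1/√46 = 0.147. With a true standardized direct effect of 0.3 or 0.4 (adversity path 0.4 to congestion and 0.3 to mood), the adjusted estimate is significant in 57% or 85% of simulated studies. The raw correlation is significant in 88% or 98%, but it also contains the adversity part, 0.4 × 0.3 = 0.12.

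**The case against.** A reader might infer that Aim 1 tests a congestion–mood hypothesis and that a link due to adversity alone would be counted as support. The documents do not say that. Aim 1 examines associations among several constructs, with adversity as one of them. The stated hypotheses belong to Aim 2, and a correlation matrix answers Aim 1 as written. The novelty sentence speaks of relating symptoms to an illness; it does not promise a relation independent of adversity. The Background also treats psychological and physical symptoms as consequences of a shared neural substrate, so a correlation running from adversity to both is itself consistent with the theory. All of this stands. The risk is one of interpretation: the raw figure could be misread.

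A reader might also infer that the planned output cannot distinguish the two explanations. That goes too far. A full matrix holds the ATES–TNSS, ATES–HADS and TNSS–HADS correlations, and the formula in Step 3 of the working needs only those three. What is missing is a commitment to report the result with its interval.

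The size is open to challenge. No document supports adversity correlations of 0.5 or 0.6 with TNSS, which also counts sneezing, itching and rhinorrhea. Entry requires current congestion of 5 or higher, which narrows the range and tends to weaken correlations.

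Confounding by age and sex might be inferred too, but no passage names either as a confounder, and the contents of the demographic form are not described.

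Finally, this is an uncontrolled pilot. Aim 4 takes the future sample size from the effect sizes of the outcome measures, not from Aim 1's correlations, and baseline adversity would not confound a randomized comparison. That limits the consequence. It does not remove the case for reporting the better estimate.

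**Conclusion.** The point holds as an optional improvement. Aim 1 omits adjustment for a variable that the protocol's own theory places upstream of both sides of the association and that is measured at the same visit. Nothing elsewhere in the plan supplies that adjustment.

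The size rests on undocumented correlations and an assumed alpha: near nominal at 0.2 to 0.3, substantial from about 0.5 upward. Adjustment removes most of the induced association, and all of it only if ATES is error-free. As described, the ATES score sums prior events, while the theory names current adversity as well, so some shared adversity may remain.

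The adjusted estimate would not establish direction, because the Brief background describes a circular process between congestion and vagal regulation.

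**What to change.** In Data Analyses, Aim 1:

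1. Keep the Pearson correlation matrix as description.
2. Add the week-0 partial correlation (or regression coefficient) of the nasal score with HADS anxiety, and separately with HADS depression, each adjusted for ATES. Report each with its 95% confidence interval beside the raw correlation.
3. State that any claim of a congestion–mood relation beyond adversity rests on the adjusted estimates.
4. Age and sex may be added as covariates if the demographic form records them.
5. Leave BPQ out of this adjustment. In the protocol's theory autonomic function lies on the path between congestion and mood, so conditioning on it could remove the relation of interest. Any model with BPQ should be separate and labelled exploratory.
6. State that the adjusted estimates do not show direction.

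The cost is one paragraph in the plan, two further estimates from data already collected, and one degree of freedom for the ATES adjustment (48 to 47 at n=50).

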The Eligibility Screening will consist of the following questions:

- 1) Are you between ages 18-99 years old? [YES TO QUALIFY]
- 2) Have you ever used the SinuSonic device? [NO TO QUALIFY]
- 3) Do you meet any of the conditions listed under the Safety and Warnings for use of the SinuSonic device? [NO TO QUALIFY]
 - a) Current or history of breathing problems (i.e., asthma, chronic obstructive pulmonary disorder (COPD), chronic bronchitis, emphysema, pneumonia, pleural effusion, lung cancer, cancer of the throat or upper airway)

- b) Current or history of circulatory problems (i.e., active nose bleed, heart arrhythmia, coronary artery disease, congestive heart failure, heart attack)
- c) Other conditions, specified as brain tumor, moderate to severe ear pain, fever greater than 101 degrees

- 4) Have you experienced symptoms of nasal congestion that have persisted at least 2 weeks? [YES TO QUALIFY]
- 5) Is your current level of nasal congestion at 5 or higher? (VAS included here) [YES TO QUALIFY]

Step 2: Consent/Linkage File

When all eligibility criteria are met, individuals will be invited to access the Informed Consent document (also provided via RedCap) to read and e-sign. Phone number and email address for the researcher will be provided in the event of questions or request for clarification.

After receiving the e-signed informed consent, researchers will assign a SubjectID number so that the participant can use the SubjectID number when completing all questionnaire assessment sessions using RedCap. Researchers will maintain a database linking SubjectID and name on their password-protected computers that will not be accessible to anyone who is not affiliated with the research.

Step 3: Pre-SinuSonic assessment

Participants will be asked to complete this assessment, via RedCap, prior to beginning use of the SinuSonic. Researchers will provide participants with a link to the assessment (text or email), along with their unique SubjectID number to use. The following instruments will be programmed into RedCap for completion:

Prior to SinuSonic Use (week 0):

- 1) Demographic Information Form
- 2) SF12 to assess overall health ("how you feel and how well you are able to do your usual activities")
- 3) TNSS to assess current nasal symptoms
- 4) BPQ to reflect perception of autonomic regulation
- 5) HADS to assess anxiety and depression
- 6) ATES to assess history of trauma/adverse events

Step 4: SinuSonic Use / Weekly assessments

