Aim 2: (*These would be the aims for a future, randomized clinical trial, with preliminary testing using data from the current feasibility/pilot study*): Evaluate the effect of the SinuSonic on users with chronic nasal congestion. We will focus on three constructs important to psychological and physical health and hypothesize that:

- A) Nasal congestion will significantly improve when comparing baseline measures to follow-up measures at each week, and will maintain effects at 5 weeks. Repeated measures ANOVA will be used to evaluate mean change in outcome measures across time in PGIC and TNSS.
- B) Autonomic functioning will significantly improve when comparing baseline measures to end of study. Repeated measures ANOVA will be used to evaluate mean change in BPQ across time.
- C) Mental health indices (depression, anxiety) will significantly improve when comparing baseline measures to end of study. Repeated measures ANOVA will be used to evaluate mean change in HADS across time.

Aim 3: (*This would be an aim for a future, randomized clinical trial, with preliminary testing using data from the current feasibility/pilot study*). Evaluate the mediating effect of current/previous adverse experiences on outcome measures at 5 weeks, using regression models.

Aim 4: Calculate effect sizes for each outcome variable, which will be necessary to determine adequate sample size for a future clinical trial. G-Power software will be used to determine sample sizes based on the effect sizes of the current outcome measures.

References

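### No age adjustment is specified for the adversity analyses: ATES counts prior events with no age scaling in adults aged 18-99, so age may confound the Aim 1 adversity correlations in either direction

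*Combined protocol and SAP*

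**What the plan says.** The Participants section sets the population: "50 adults (aged 18-99 years) with self-reported nasal congestion will be recruited for the study". Age is screened with a single yes/no item, "Are you between ages 18-99 years old? [YES TO QUALIFY", so screening does not capture age as a number. At week 0 participants complete a "Demographic Information Form", whose items are not listed.

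Under Description of Measures, the ATES paragraph gives the content: "This measure asks about childhood adverse experiences, childhood maltreatment, other person maltreatment, life-threatening situations, sudden deaths of close ones, and personal health situations". The score is built from part of that content. Reported prior events "of maltreatment, life-threatening situations, and sudden deaths of close ones are summed to create an adversity score (range: 0–19". No look-back window and no scaling by age are stated. ATES is given once, before device use.

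Data Analyses, Aim 1 lists adverse events among the baseline measures to be related to one another. Its method is one sentence: "Pearson correlation analyses will be used to evaluate relationships among measures at each timepoint". It names no partial correlation and no covariate. Aim 3 reads "Evaluate the mediating effect of current/previous adverse experiences on outcome measures at 5 weeks, using regression models" and lists no model terms. Neither age nor any other demographic variable appears in any of the four aims.

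**The concern.** A count of prior events depends partly on how long a person has had to experience them. Life-threatening situations and sudden deaths of close ones can go on accruing through adult life, and time at risk here may differ between participants by decades. Some of the spread in ATES may therefore reflect age. If anxiety, depression, autonomic reactivity or nasal symptoms also vary with age, the raw correlation of ATES with that score is shifted: away from zero if the age pattern runs in the same direction as the adversity link, towards zero if it runs against it.

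This matters because adversity is part of the study's rationale. The purpose statement puts adverse events in the first aim, and the background proposes that earlier adversity feeds a cycle of congestion, poor vagal regulation and mood symptoms. The aims are also meant to show whether a larger randomized trial is warranted. An adversity correlation is thus likely to be read as support for the mechanism, and that reading is less safe if an age pattern could produce or hide it.

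**Working it through.** The documents state no expected correlation, alpha, power or sample-size calculation, so there is no figure of the plan's to reproduce. The check asks how far age could move a raw correlation.

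**From the documents:** N = 50; ages 18 to 99; ATES an unscaled sum, 0 to 19; Pearson correlation for Aim 1.

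**Assumed:** a = correlation of age with ATES; b = correlation of age with the outcome score; p = correlation of ATES with the outcome at fixed age; linear age effects; two-sided alpha 0.05; all 50 participants with both measures.

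**Formula.** Raw r = p × √[(1 − a²)(1 − b²)] + a × b. With no link at fixed age (p = 0), raw r = a × b.

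Rejection rates use Fisher's z: atanh(r) × √(N − 3) compared with ±1.96, where √47 = 6.856.

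**Worked examples**
- p = 0, a = b = 0.2: r = 0.2 × 0.2 = 0.04.
- p = 0, a = 0.4, b = 0.3: r = 0.4 × 0.3 = 0.12.
- p = 0.30, a = 0.4, b = −0.3: √(0.84 × 0.91) = 0.874; 0.30 × 0.874 − 0.12 = 0.142.
- p = 0.30, a = 0.4, b = +0.3: 0.30 × 0.874 + 0.12 = 0.382.

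| a | b | raw r if p = 0 | false-positive rate | raw r if p = 0.30 |
|---|---|---|---|---|
| 0.2 | 0 | 0 | 5.0% | 0.294 |
| 0.2 | 0.2 | 0.04 | 5.9% | 0.328 |
| 0.2 | −0.2 | −0.04 | 5.9% | 0.248 |
| 0.3 | 0.3 | 0.09 | 9.5% | 0.363 |
| 0.3 | −0.3 | −0.09 | 9.5% | 0.183 |
| 0.4 | 0.3 | 0.12 | 13.1% | 0.382 |
| 0.4 | −0.3 | −0.12 | 13.1% | 0.142 |

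When p = 0.30, the partial correlation has power of about 56%. The raw correlation has power of about 17% at r = 0.142, 25% at 0.183 and 79% at 0.382.

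**Check by simulation** (20,000 runs per case, N = 50). At a = b = 0.3 the raw test rejected in 9.3% of runs, and at a = 0.3, b = −0.3 in 9.8%. The age-adjusted test rejected in 4.9% and 5.2%.

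**Price of adjusting.** The critical |r| moves from 0.279 (48 df) to 0.282 (47 df). Power at r = 0.40 moves from 82.8% to 81.9%.

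**The case against.** A reader might infer that the count can only rise with age, so that the adversity results are bound to be mixed with age. The documents do not support that.

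- A person's true cumulative count cannot fall, but Aim 1 compares different people. The instrument also asks about childhood adversity and maltreatment, which are fixed in any adult, and nothing excludes childhood maltreatment from the summed score. The score rests on recall, and cohorts may differ. How many of the 19 points can accrue in adulthood is not stated.
- Confounding needs age to be related to both ATES and the outcome. The documents give neither correlation.

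A reader might also take Aim 3 to be unadjusted by design. It is not: the plan says only that regression will be used and lists no terms. The gap there is an unspecified model.

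Three further points have weight. Aim 1 is worded as examining associations in a pilot, and a raw r is a valid description of that. Making the partial correlation the main result would change the quantity to adversity relative to age peers, which is debatable. Next, the larger effects above lie at the edge of an assumed grid, and sampling error is large. At N = 50 the 95% CI around r = 0.30 is tanh(0.3095 ± 1.96/6.856), about 0.02 to 0.53, which contains even the shifted value of 0.142. Lastly, Aim 4 bases sample sizes on the outcome measures, and Aim 2 tests changes over time without using ATES, so neither depends on these correlations.

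What remains is narrower: nothing in the plan would let a reader tell an adversity link from an age pattern.

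**Conclusion.** The gap is real and minor. Aim 1 specifies only unadjusted Pearson correlations for an event count with no age scaling, in a sample open to ages 18 to 99, so age may confound the adversity pairs in either direction. The size is unknown. Under small assumed age correlations (0.2 and 0.2) the distortion is slight: a spurious r of 0.04 and a 5.9% false-positive rate against a nominal 5%. At 0.4 and 0.3 it reaches 0.12 and about 13%. With age correlations of opposite sign, an age-adjusted link of 0.30 could appear as low as 0.14 on the same grid. With age unrelated to the outcome there is no spurious correlation. All of this assumes linear age effects and complete data on 50 participants. No stated figure is wrong, and the raw correlation stands as a description. The weakness lies in reading it as evidence for the mechanism.

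**What to change.** 1. Data Analyses, Aim 1: for each pair that includes ATES, report the partial correlation adjusted for age in years, with its 95% CI, beside the raw Pearson r. State that an adversity link that disappears after adjustment will not be interpreted as support for the mechanism.
2. Data Analyses, Aim 3: include age in years as a covariate when the regression models are written out.
3. Step 3: confirm that the week-0 demographic form records age in years, because screening records only whether the participant falls within the permitted range.

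The cost is a few sentences of text, one degree of freedom out of about 50 and at most one item on a form already in use. No extra visits or participants are needed. Item 3 should be settled before data collection, since age may not be recoverable afterwards.

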After completing the pre-SinuSonic assessment, researchers will inform participants to begin directed use of the SinuSonic (2 minutes per day, 2 times per day). Participants will be asked to confirm SinuSonic use on a weekly questionnaire. Additionally, participants will be asked to complete the following questionnaires approximately 5 minutes after final SinuSonic use for that week. The following instruments will be programmed into RedCap for completion:

Weekly, for 4 weeks (end of week 1, 2, 3, 4).

- 1) TNSS to assess current nasal symptoms
- 2) PGIC to reflect change in activity limitations, symptoms, emotions and overall quality of life

Step 5: Final research assessment

Participants will be asked to confirm use of the SinuSonic on a weekly questionnaire. Additionally, participants will be asked to complete the following questionnaires approximately 5 minutes after final SinuSonic use on the 5th consecutive week. The following instruments will be programmed into RedCap for completion:

End of Study (end of week 5).

- 1) TNSS to assess current nasal symptoms
- 2) PGIC to reflect change in activity limitations, symptoms, emotions and overall quality of life
- 3) BPQ to reflect perception of autonomic regulation
- 4) HADS to assess anxiety and depression

Description of Measures

Body Perception Questionnaire (BPQ) (Cabrera et al., 2018). The Body Perception Questionnaire (BPQ) is a self-report measure of body awareness and autonomic reactivity. Its items are based on the organization of the autonomic nervous system (ANS), a set of neural pathways connecting the brain and body. These pathways send information from the body about the status of organs and tissues (i.e., afferent projections). Some of these incoming signals form a basis for the subjective awareness of the body. The ANS also carries signals that control the functions of these organs and tissues (i.e., efferent projections). These signals can alter the functions of the body, depending on internal and external needs. Only the Autonomic Reactivity subscale will be distributed and used for the current study.

Hospital Anxiety and Depression Scale (HADS) (Zigmond & Snaith, 1983). HADS is a fourteen-item scale with seven items each for anxiety and depression subscales. Scoring for each item ranges from zero to three. A subscale score >8 denotes anxiety or depression.

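### Hypothesis A claims improvement at every week, maintained at week 5, but the only named test, an omnibus repeated measures ANOVA, has no direction and identifies no week

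*Combined protocol and SAP*

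**What the plan says.** Aim 2 A in the Data Analyses section states the hypothesis: "Nasal congestion will significantly improve when comparing baseline measures to follow-up measures at each week, and will maintain effects at 5 weeks". The analysis follows in one sentence: "Repeated measures ANOVA will be used to evaluate mean change in outcome measures across time in PGIC and TNSS".

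TNSS is in the week 0 battery (Step 3), in the weekly battery for weeks 1 to 4 (Step 4) and in the end-of-study battery at week 5 (Step 5), which gives six means. PGIC is in the weekly and week 5 batteries but not in the week 0 battery, which gives five means and no baseline.

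On sample size the Participants section says only: "50 adults (aged 18-99 years) with self-reported nasal congestion will be recruited for the study". The plan gives no significance level, week-versus-baseline contrast, direction, definition of maintenance or rule for handling several weeks. Aim 2 is described as preliminary testing for a later randomised trial. The Data Analyses section says the aims will help decide whether that trial is justified, and Aim 4 reads: "Calculate effect sizes for each outcome variable, which will be necessary to determine adequate sample size for a future clinical trial".

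**The concern.** The hypothesis is directional and tied to particular weeks: five comparisons with baseline, each towards improvement, plus a statement about week 5. The time effect of a repeated measures ANOVA is a single test that the means are all equal. It rejects for any departure from equality, including a benefit that has gone by week 5 and a worsening.

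If its p-value is taken as the result for hypothesis A, a short-lived change could be reported as a maintained one. That conclusion would then feed the decision on a larger trial. An effect size attached to the omnibus time effect could also be large when the week 5 change is zero.

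For PGIC the test compares follow-up weeks with one another. If every participant gave the same favourable rating at all five weeks, there would be no time effect to detect.

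**Working it through.** The plan states no power or sample-size figure, so there is none to reproduce. The check asks how often the named test is significant when hypothesis A is false.

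**Inputs from the plan.** n = 50 (Participants); six TNSS time points, weeks 0 to 5 (Steps 3 to 5).

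**Inputs assumed, because the plan gives none.** Two-sided alpha 0.05; equal correlation ρ between any two weeks of 0.3, 0.5 or 0.7; effects in units of the between-person SD; complete data.

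**Omnibus test.** With k = 6 means, the time effect has 5 and 5 × (50 − 1) = 245 degrees of freedom. Power comes from the noncentral F distribution with λ = n × S / (1 − ρ), where S is the sum of squared deviations of the six means from their average.

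**Benefit at weeks 1 and 2 only.** The means are 0, −e, −e, 0, 0, 0 and their average is −e/3.
- S = 2 × (2e/3)² + 4 × (e/3)² = 4e²/3.
- For e = 0.4, S = 4 × 0.16 / 3 = 0.2133.
- At ρ = 0.5, λ = 50 × 0.2133 / 0.5 = 21.3, which gives 96%.

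| Size of early-only benefit | ρ = 0.3 | ρ = 0.5 | ρ = 0.7 |
|---|---|---|---|
| 0.4 SD | 86% | 96% | 99.9% |
| 0.3 SD | 59% | 76% | 95% |
| 0.2 SD | 27% | 38% | 61% |

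In every cell the true week 5 change is zero. With n = 40 the 0.4 SD, ρ = 0.5 cell is 90%.

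**Direction.** S contains only squared deviations, so reversing the sign of every change leaves λ unchanged. For a sustained 0.4 SD change at weeks 1 to 5:
- S = (5/6) × 0.16 = 0.1333.
- At ρ = 0.5, λ = 50 × 0.1333 / 0.5 = 13.3, which gives 81% whether symptoms improve or worsen.

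**Check by simulation.** This used a Greenhouse-Geisser correction, n = 50 and 4,000 runs per scenario. With a 0.5 SD benefit at weeks 1 and 2 only, the omnibus test was significant in 97%, 99.8% and 100% of runs at ρ = 0.3, 0.5 and 0.7. With autoregressive correlation 0.7 it was 99%. In the same data, the paired contrast of week 5 with week 0 indicated improvement in only 2 to 3% of runs.

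**PGIC.** There are five means (weeks 1 to 5) and therefore 4 numerator degrees of freedom. No contrast among them involves week 0.

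**The case against.** The strongest reply is that the plan never says a significant omnibus F establishes hypothesis A. The hypothesis sentence describes comparisons with baseline week by week, those contrasts can be requested within the ANOVA procedure, and competent investigators would look at the weekly means. On this reading the defect is only that the contrasts are unspecified. That stands as far as intent goes. It does not remove the problem, because the ANOVA is the only analysis named and nothing ties the words about each week and about maintenance to a test.

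It is also fair that this is preliminary testing in a pilot with no numerical go/no-go threshold, and that a later randomised trial needs a between-group difference, which a single-arm change does not supply. Both points limit the severity.

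Two stronger readings are tempting, and the documents do not support them.

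- **Serious multiplicity inflation.** A reader might infer a family-wise error of 1 − 0.95⁵ = 22.6% from five weekly tests. That figure needs independent tests, and these share one baseline. Simulation gives about 18 to 19%, and only if any single week could be claimed. The plan does not say so; its wording requires every week, and requiring all five does not inflate the error.
- **The ANOVA costs power.** A reader might infer that a week 5 contrast is more powerful. That holds for a steady linear decline (79% against 72% for a fall reaching 0.4 SD at week 5, ρ = 0.5). For the sustained 0.4 SD benefit that hypothesis A describes, the omnibus test has 64%, 81% and 97% power at ρ = 0.3, 0.5 and 0.7, and the contrast 65%, 79% and 95%. The two are essentially equal.

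**Conclusion.** The concern holds as a mismatch between claim and test. For TNSS the named test is neither directional nor week-specific. It is significant in 27% to 99.9% of trials over the assumed range when the benefit has vanished by week 3, and it cannot tell sustained improvement from sustained worsening. For PGIC the named test cannot address change from baseline at all.

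The percentages rest on assumed effect sizes, correlations, alpha and complete data. The lack of direction, the lack of a named week and the PGIC point need none of these assumptions. The case for change is that the test does not answer the question, not that it lacks power or inflates the error rate. The matter should be corrected, at modest severity given the pilot setting.

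**What to change.** In Aim 2 A:

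- Base the claim on the TNSS change from week 0 to week 5: a paired contrast, two-sided 0.05, reported as an estimate with a 95% CI.
- Report the contrasts of weeks 1 to 4 with week 0, each with a 95% CI, as supporting results. Claim improvement at each week only if all five contrasts are significant in the improving direction.
- Do not use the omnibus F alone as the basis for the claim.
- Report PGIC at week 5 against its no-change category, not as change from week 0.

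This takes a few sentences and uses the same data and software. A fixed testing order over the weeks is another valid choice but is not needed.

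There are two costs. An early-only effect would be reported but would not support the lead claim. The all-weeks claim is also harder to reach: for a sustained 0.5 SD benefit at n = 50, simulation gives 57%, 79% and 98% at ρ = 0.3, 0.5 and 0.7, against 83%, 94% and 99.8% for the week 5 contrast alone.
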